7.4.3.5. Time to Testosterone Recovery

Testosterone levels will be followed for up to 90 days in approximately 100 patients randomized to relugolix and approximately 50 patients randomized to leuprolide acetate who complete 48 weeks of treatment and who do not plan to start alternative androgen deprivation therapy within the following 12 weeks (or within 24 weeks following the last injection of leuprolide acetate). As the enrollment for the follow-up of testosterone recovery has been completed for the patients enrolled under protocol amendment 2, analysis of time to testosterone recovery will be performed in the primary analysis and there will be no updates in the final analysis.

Patients will be censored at the time of last follow-up visit or initiation of treatments known to suppress testosterone (refer to [Appendix Table 1](#)), whichever comes earlier.

Time to testosterone recovery will be summarized using the Kaplan-Meier method with the following 3 testosterone recovery levels:

- ≥ 50 ng/dL (1.7 nmol/L);
- Above baseline level or 280 ng/dL;
- Above 280 ng/dL (as one of the key secondary endpoints).

Cumulative incidence of time to testosterone recovery at the 30-day, 60-day and 90-day follow-up visits will be estimated by treatment group along with 95% CI.

The unstratified test via log-log transformation of the difference in cumulative incidence of time to testosterone recovery back to 280 ng/dL will be compared at the 90-day follow-up visit (unstratified test version as in Section 7.4.3.1).

7.4.3.6. Time to Prostate-Specific Antigen Progression

Prostate-specific antigen progression is defined per Prostate Cancer Clinical Trials Working Group 3 Guidelines ([Scher et al, 2016](#)) as the following:

1. With declining PSA from baseline: The first increase in PSA of $\geq 25\%$ and ≥ 2 ng/mL above the nadir with confirmation by a consecutive PSA measurement at least 3 weeks later.

The date of initial PSA progression will be considered as the date of event for the Kaplan-Meier analysis.

The initial PSA progression can be confirmed with later PSA measurements as long as all PSA values in between from the initial PSA progression indicated PSA progression. For example, patient had initial PSA progression at Day 78, the second PSA progression at Day 92, and the third PSA progression at Day 106. The patient will be considered as having PSA progression at Day 78 with confirmation at Day 106.

2. Without declining PSA from baseline: PSA increase of 25% or greater and 2 ng/mL from baseline beyond Week 12 (> 84 days after the date of the first dose).

Patients without confirmed PSA progression will be censored at the last available assessment prior to the follow-up visits. As a sensitivity analysis, patients will be censored at the last available assessment prior to the follow-up visits or at the time of initiating any treatment that can affect or alter PSA levels (refer to [Appendix Table 2](#)), whichever comes earlier.

Time to PSA progression is defined as the time from the date of first dose to the date of the initial PSA progression which was subsequently confirmed and will be analyzed using the Kaplan-Meier method. Treatment comparison via hazard ratio will be performed using Cox proportional hazard model.

7.4.3.7. Castration Resistance Free Survival

Castration resistance free survival will not be analyzed for the primary analyses but will be analyzed at the final analyses when approximately 390 patients with metastatic disease have been randomized to the study and have had the opportunity to be evaluated for 48 weeks of study treatment and completed the 30-day safety follow-up or discontinued early.

Castration resistance free survival is in the key secondary endpoints and will be analyzed under metastatic patients only and mITT population. PSA results and deaths from follow-up visits will be excluded from the analysis. Patients with metastatic disease will be identified through presence of distant metastasis (M1) at study entry reported in the CRF. If the discrepancy between IWRS and CRF is $> 5\%$, sensitivity analysis based on the presence of metastatic disease reported in the IWRS will be performed.

Castration resistance free survival is defined as the time from the date of first dose to the date of PSA progression while castrated or death due to any reason, whichever occurs earlier. A confirmed PSA progression prior to testosterone escape or the date of testosterone censoring will be considered as an event. Patients will be censored at the last PSA assessment prior to follow-up visits, the date of censoring for testosterone, or the date of testosterone escape, whichever comes earlier.

As a sensitivity analysis, patients will be censored at the last available assessment prior to the follow-up visits, the date of censoring for testosterone, the date of testosterone escape, or the time of initiating androgen receptor inhibitors (eg, enzalutamide), whichever comes earlier.

Castration resistance free survival will be analyzed using the Kaplan-Meier method. Treatment comparison with hazard ratio will be performed using Cox proportional hazard model and p-value will be provided using unstratified log-rank test on patients with metastatic disease and stratified log-rank test on mITT population. Proportionality in survival curves between two treatment groups will be assessed. CRFS rate at Week 49 Day 1 (Day 337) will be estimated along with 95% CI.

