7.3.1.2. Kaplan-Meier Analysis and Censoring Rules

In general, patients with testosterone escape (any testosterone test result rising above the castration level [≥ 50 ng/dL]) from Week 5 Day 1 through Week 49 Day 1 will be considered as an event in the Kaplan-Meier analysis. The time from the date of the first dose to date of the first testosterone escape will be considered as the event time.

Patients who have not reached castration level at Week 5 Day 1 will be considered as having had an event at the target day of Week 5 Day 1.

Patients who discontinued from the study prior to Week 5 Day 1 will be censored at the target day of Week 5 Day 1. In addition, patients without a Week 5 Day 1 assessment will be considered to have had an event at the target day of Week 5 Day 1.

For patients reaching castrate levels at Week 5 Day 1, the following rules will be applied to the Kaplan-Meier analysis for estimation of sustained castration rate with consideration for missed visits. Time to event or censoring, whichever occurs first, will be used in Kaplan-Meier analysis.

- a) Patients who had one or more consecutive missed visits (ie, a visit gap of > 42 days) and had a non-castrate assessment immediately after the missed visit(s) will be considered as having an escape at the target day of the earliest missed visit prior to the non-castrate assessment;
- b) Patients with one missed visit who has a castrate assessment immediately before and after the missed visit will be assumed to be castrated at the missed visit;
- c) Patients with two or more consecutive missed visits (ie, a visit gap of > 70 days) and who had a castrate assessment immediately before and after the missed visits will be censored at the last available testosterone assessment prior to the missed visits.

Note: A visit gap of 70 days for two missed visits was used to consider the duration between two expected visits (8 weeks), plus the visit windows allowed per protocol (7 days for each

expected visit with a total of 2 weeks as visit window for two visits). A visit gap of 42 days for one missed visit was used to consider the visit of every 4 weeks, and ± 7 days as the visit window, per protocol.

Otherwise, patients will be censored at the last available assessment prior to the follow-up visits, including patients who discontinue from the trial for reasons other than a non-castrate testosterone level.

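### The CRFS event rule does not fully enforce castration: it sets no testosterone condition on a PSA rise before Day 29, and none on the confirming PSA sample

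*SAP*

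**What the plan says.** **Definition.** SAP Section 7.4.3.7 gives the CRFS definition in these words: "the time from the date of first dose to the date of PSA progression while castrated or death due to any reason, whichever occurs earlier". The sample size text in Section 2.2 describes the events in the same terms.

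**Event and censoring rule.** The same section puts this into practice as "A confirmed PSA progression prior to testosterone escape or the date of testosterone censoring will be considered as an event". Otherwise the patient is censored at the earliest of the last PSA before the follow-up visits, "the date of censoring for testosterone, or the date of testosterone escape, whichever comes earlier".

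**Escape.** Under Section 7.3.1.2, a testosterone result of 50 ng/dL or more "from Week 5 Day 1 through Week 49 Day 1 will be considered as an event in the Kaplan-Meier analysis". For the Week 5 visit, "Patients who have not reached castration level at Week 5 Day 1 will be considered as having had an event at the target day", that is Day 29. The Week 5 window runs from Day 22 to Day 43 (Table 2 and Section 7.3.1.1).

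**PSA progression.** Section 7.4.3.6 has two pathways. After a PSA decline, progression is a rise of at least 25% and 2 ng/mL above nadir, "with confirmation by a consecutive PSA measurement at least 3 weeks later", with every value in between also showing progression. Its date is fixed as follows: "The date of initial PSA progression will be considered as the date of event for the Kaplan-Meier analysis". Without a decline, progression can be declared only after Day 84.

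**Sampling and role.** Testosterone and PSA are both assessed at Day 4, Week 3, Week 5 and then monthly (Section 2.1). CRFS is tested twice in the fixed sequence (Table 4), in metastatic patients and in all patients.

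**The concern.** Preceding a recorded escape is not the same as being castrate. The two agree only where the escape rule is active and only for the sample it is applied to. The escape rule starts at Day 29, whereas CRFS time starts at first dose. The escape date is compared with a progression date taken from the first of two PSA samples, and the second sample carries no testosterone condition.

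A PSA rise in a man whose testosterone is not suppressed, or a rise confirmed only once suppression has failed, is not clearly castration resistance. If such rises count, the endpoint departs from its own definition. If the text can be read two ways, two programmers can derive different event sets for two alpha-protected tests.

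**Working it through.** **The plan's own figure.** Inputs from Section 2.2: 107 events, hazard ratio 0.55, 2:1 allocation, two-sided 5%, stated power 85%. By the Schoenfeld formula:

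- z = sqrt(107 × 2/9) × |ln 0.55| − 1.96 = 4.876 × 0.598 − 1.96 = 0.955, so power = 83.0%. This is within 2 points of the stated value.
- With 130 and 260 metastatic men, exponential times, 60% of controls event-free at 48 weeks, and 15% dropout spread over 48 weeks, the expected events are about 48 on leuprolide and 59 on relugolix, 107 in total.

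**Tracing the rules over the visit schedule.** Scheduled PSA and testosterone days are 4, 15, 29, 57, 85, 113 and so on. A rise at Day 15 cannot be confirmed at Day 29 (14 days later). Day 15 + 21 = Day 36, so the next scheduled visit that can confirm it is Day 57. Reading I requires only the initial rise to precede escape. Reading II requires the confirmation to precede it too.

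| Case | Testosterone (ng/dL) | Initial rise | Confirming PSA | Escape date | Reading I | Reading II |
|---|---|---|---|---|---|---|
| A | ≥ 50 at Day 15, < 50 from Day 29 | Day 15 | Day 57 | none | event, Day 15 | event, Day 15 |
| B | ≥ 50 at the Week 5 sample, drawn Day 25 | Day 25 | Day 46 or later | Day 29 | event, Day 25 | censored, Day 29 |
| C | never < 50 | Day 15 | Day 57 | Day 29 | event, Day 15 | censored, Day 29 |
| D | < 50 through Day 57, ≥ 50 at Day 85 | Day 57 | Day 85 | Day 85 | event, Day 57 | censored, Day 85 |
| E | < 50 through Day 57, ≥ 50 at Day 85 | Day 85 | Day 113 | Day 85 | censored, Day 85 | censored, Day 85 |

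- Case E shows the rule working: from Day 29, a rise first seen with non-castrate testosterone is not an event.
- Case A is gap 1 alone. Under either reading the event is dated to a sample at which testosterone was not castrate.
- Case B shows the effect of the target-day convention. The sample that shows both the PSA rise and the non-castrate testosterone is from Day 25, but its escape is dated Day 29, so the rise appears to come first.
- Case D is gap 2 alone. Case C needs both gaps.

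**How narrow gap 1 is.** The no-decline pathway cannot contribute, since it starts after Day 84. With on-target samples, gap 1 needs a PSA fall by Day 4, a rise of at least 25% and 2 ng/mL above nadir at Day 15, and progression sustained through Day 57. A Week 5 sample drawn on Days 22 to 28 is the other way in.

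**Size.** The SAP gives no rate for any of these patterns. As an assumption only, if 5, 10 or 20 of the 107 events did not qualify and the hazard ratio stayed at 0.55, power from 102, 97 or 87 events would be 81.2%, 79.3% or 74.8%.

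**The case against.** The strongest reply is that little is left once the text is read as a whole. From Day 29 the escape and censoring rules, with testosterone and PSA taken at the same visits, do impose castration on the initial rise. The event sentence follows directly on a definition that requires castration, so it can fairly be read as requiring the confirmation before escape as well; the initial-date rule in Section 7.4.3.6 then only sets the date. On that reading cases B, C and D disappear. The man in case A still has a progressing PSA under castrate testosterone at Days 29 and 57, so it is his event date rather than his status that is doubtful.

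Much of this stands. A reader might infer that the SAP never asks for castrate testosterone; it does, for an initial rise from Day 29. A reader might infer that every affected event is false; case A shows otherwise. What does not fall away is that the SAP never chooses between the two readings, and that case A is dated before castration under both.

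A reader might also infer a bias towards relugolix, on the view that the agonist suppresses testosterone later. The SAP does not say this. It treats the early castration rates as hypotheses to be tested (Section 7.4.3.1). Nor do the planning rates give a direction. Failure rates of 4% and 6% (Section 2.2) give 0.04 × 130 = 5.2 leuprolide and 0.06 × 260 = 15.6 relugolix men failing suppression for any reason, whatever their PSA. Using crude event ratios:

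- 5 false events on leuprolide alone: 0.55 × 48/53 = 0.50.
- 5 on leuprolide and 16 on relugolix: 0.55 × (75/59) / (53/48) = 0.63. A split of 45 and 62 events gives 0.62.

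The sign depends on which men are assumed affected. These counts are not even a bound, because men castrate late but by Day 29 (case A) are not among them.

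**Conclusion.** The point holds in a limited form. The CRFS event rule does not fully deliver its own definition. It has no castration condition on an initial rise before Day 29, and it does not say whether the confirming PSA must precede escape. The first gap is certain from the text but confined to a fall-then-rise pattern in the first four weeks. The second is an ambiguity, not a proven contradiction.

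The number of men affected cannot be derived from the SAP and the net direction is unknown, so no shift in the hazard ratio should be claimed. The power figures above rest on assumed counts. The correction is worth making because CRFS supports two alpha-protected tests and is analysed only at the final analysis, so the derivation can be settled before then at little cost.

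**What to change.** In Section 7.4.3.7, count a PSA progression as a CRFS event only if both the initial and the confirming PSA samples fall on or after the first testosterone result below 50 ng/dL and before testosterone escape or testosterone censoring. Specify in addition:

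- Castrate status between visits follows the missed-visit rules of Section 7.3.1.2. Do not use a fixed 28-day look-back: that section treats gaps of up to 42 days as not missed and assumes castration across a single missed visit.
- A non-castrate Week 5 result is ordered against PSA by its actual sample date, not the Day 29 target.
- A rise that fails the condition is not an event on that date. The patient stays at risk, a later qualifying pair of samples may count, and otherwise he is censored under the existing rule (escape, testosterone censoring or last PSA, whichever is earliest).
- Ties: say whether a confirming PSA drawn on the same day as the last castrate testosterone qualifies. Otherwise a progression confirmed at the Week 49 visit could be lost, because testosterone is censored on that day.

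The cost is SAP wording and a merge of testosterone with PSA, which share a visit schedule. The downside is possibly a few fewer CRFS events.

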2.2. Sample Size Justification

The following assumptions were used to determine the sample size for this study:

- True probabilities of sustained testosterone suppression are 94% and 96% for relugolix and leuprolide acetate, respectively;
- 2:1 randomization ratio (relugolix: leuprolide acetate);
- Dropout rate: 15%.

For Evaluation Criterion 1, 610 patients in the relugolix group will provide approximately 90% power to rule out a fixed probability of sustained testosterone suppression of < 90% at a two-sided type I error rate of 0.05.

For Evaluation Criterion 2, with a noninferiority margin of -10% and an overall two-sided type I error rate of 0.05, a total of approximately 915 patients (610 receiving relugolix, 305 receiving leuprolide acetate) will yield at least 99% power to declare the noninferiority of relugolix to leuprolide acetate. The 10% noninferiority margin for the comparison of relugolix versus

leuprorelin is based on regulatory precedence of pivotal assessment of gonadotropin-releasing hormone (GnRH) antagonist degarelix versus leuprorelin as well as studies of branded GnRH agonist generics.

The primary analysis will be performed separately for each evaluation criterion using data collected through 48 weeks after enrollment of approximately 915 patients.

Approximately 915 patients will be randomized in order to fulfill the regulatory requirements of all participating countries included in the primary efficacy endpoint of this study.

Under amendment 3 the study is also powered for the secondary endpoint of castration resistance free survival in the high-risk subgroup of patients with metastatic disease, although this is not part of the primary analysis. Approximately 107 confirmed castration-resistance events (ie, PSA progression while castrated or deaths due to any reasons) will need to be observed (or approximately 390 patients with metastatic disease will need to be enrolled) to detect a hazard ratio of 0.55 (relugolix vs. leuprolide acetate) with 85% power and a two-sided type I error of 5%, assuming a castration-resistant event-free rate of 60% at 48 weeks for the control arm, an 18-month enrollment period, 12 months of additional follow-up, and a 15% dropout rate.

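### CRFS is censored permanently at escape and missed-visit dates built for the primary endpoint, so progressions and deaths that meet its own definition are dropped; the event loss is small, but the rule needs its own wording

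*SAP*

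**What the plan says.** **Definition and censoring.** Section 7.4.3.7 makes the event "PSA progression while castrated or death due to any reason". It counts a confirmed PSA progression only if it precedes testosterone escape or testosterone censoring. Follow-up ends at the earliest of the last PSA before the follow-up visits, "the date of censoring for testosterone, or the date of testosterone escape, whichever comes earlier". It adds that "PSA results and deaths from follow-up visits will be excluded from the analysis".

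**Where those dates come from.** Section 7.4.3.7 gives no cross-reference. The only definitions are in Section 7.3.1.2:
- an escape is any result of 50 ng/dL or more from Week 5 Day 1 on, with no confirmation and no return after re-suppression;
- rule (a) back-dates an escape to the earliest missed visit when the next value is non-castrate;
- rule (c) censors before a gap of two or more visits even when the values on both sides are castrate;
- a non-castrate Week 5 result is an event at Day 29, and "patients without a Week 5 Day 1 assessment will be considered to have had an event" on the same day.

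**Planning.** Section 2.2 sets a target of "Approximately 107 confirmed castration-resistance events", which it equates with enrolling about 390 men who have metastases. The design uses a hazard ratio of 0.55, power of 85% and a two-sided 5% level. Its control-arm premise reads "assuming a castration-resistant event-free rate of 60% at 48 weeks for the control arm". It allows 15% dropout and makes no separate allowance for escape censoring.

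**Status.** Table 4 places CRFS in the fixed testing sequence at the final analysis, in metastatic patients and then in all patients.

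**The concern.** The definition asks whether a man was castrate when his PSA progressed. The censoring rule asks whether he had been castrate at every visit since Week 5, with no missed-visit gap. These are different questions. Take a man with one value of 55 ng/dL at Week 17, castrate from Week 21, whose PSA progresses at Week 33 with castrate testosterone. He meets the definition but is censored at Week 17. The definition puts no castration condition on death, yet the censoring sentence makes no exception for a death after an escape.

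Counting a missing or back-dated result as a failure is conservative for the primary endpoint. In CRFS the same imputation is not a failure; it only ends observation. If incompletely suppressed men, or men who miss visits, have a different risk of progression, the censoring is informative. The SAP's planning failure rates also differ by arm (6% and 4%).

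Nothing in the plan tests this for CRFS. Its one sensitivity analysis of censoring adds a further reason to censor. The primary endpoint, by contrast, has Sensitivity Analysis 4 for delayed suppression.

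A second, separate question is whether a PSA rise first seen at Week 49 can ever become a confirmed event.

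**Working it through.** **1. Inputs (SAP Sections 2.1 and 2.2).** 390 metastatic patients at 2:1, so 260 relugolix and 130 leuprolide; control event-free rate 60% at 48 weeks (336 days); hazard ratio 0.55; dropout 15%; sustained suppression 94% and 96%, so failure by Day 337 is 6% and 4%.

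**2. Reproducing the plan's figure.** With exponential event and dropout times:
- control hazard h = −ln(0.60)/336 = 0.001520 per day; relugolix 0.55 × 0.001520 = 0.000836;
- dropout hazard g = −ln(0.85)/336 = 0.000484;
- P(event) = h/(h+g) × [1 − exp(−(h+g)T)], with T = 336.

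Control: 130 × 0.3717 = 48.3. Relugolix: 260 × 0.2269 = 59.0. Total **107.3 events**. This agrees with Section 2.2, read as a fixed 48-week window.

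**3. Power baseline.** Schoenfeld at 2:1: power = Φ(√(d × 2/9) × |ln 0.55| − 1.96). For d = 107: √23.78 × 0.5978 − 1.96 = 0.955, giving **83.0%**. The Freedman formula for 1:1 allocation gives exactly 107 events for 85% power, while Schoenfeld at 2:1 asks for 114. The comparisons below therefore start from 83%, not 85%.

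**4. Adding escape censoring at 6% and 4%.**
- Spread over 48 weeks (add −ln(0.94)/336 and −ln(0.96)/336 to g): 57.3 + 47.5 = 104.8 events, power 82.3%.
- All at Week 5 (those shares contribute only 28 days): 260 × (0.94 × 0.2269 + 0.06 × 0.0230) + 130 × (0.96 × 0.3717 + 0.04 × 0.0414) = 55.8 + 46.6 = 102.4 events, power 81.4%.

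The loss is about 2.5 to 5 events and 1 to 2 power points.

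**5. If missing Week 5 samples also censor.** The SAP gives no rate, so these are assumptions, each added to spread escapes:

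| Assumed share, each arm | Events | Power |
|---|---|---|
| 2% | 102.9 | 81.6% |
| 5% | 100.1 | 80.5% |
| 10% | 95.5 | 78.6% |

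A man censored at Day 29 loses (337 − 29)/7 = 44 weeks of follow-up.

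**6. Week 49 rises.** Section 7.4.3.6 requires confirmation at least 3 weeks later where PSA has declined from baseline. The last scheduled on-treatment visits in Table 2 are Days 309 and 337, and follow-up PSA is excluded. A rise first seen at Day 337 therefore has no later scheduled value that could confirm it. If the 60% rate does not already allow for this, set T = 308 (events first seen by the Week 45 visit):

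| Case | Events | Power (2:1 Schoenfeld) |
|---|---|---|
| Week 49 rule alone | 45.4 + 55.0 = 100.4 | 80.6% |
| Plus escapes, spread | 98.3 | 79.8% |
| Plus escapes, all at Week 5 | 95.9 | 78.8% |

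These figures treat every event as a PSA rise needing confirmation. If 5% of events are deaths (assumption), the last two become 98.6 and 96.2.

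**The case against.** **A reader might infer that 390 patients cannot yield 107 events.** The document does not support that. Its inputs give 107.3, both figures are stated as approximate, and escape censoring at its own rates removes at most about 5. A fall from 85% to 78% power would also mix two formulas, since 107 events give 83% on the formula that yields the lower number.

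**A reader might also infer that a missed Week 5 sample is definitely an escape for CRFS.** Section 7.3.1.2 calls it an event and keeps the word escape for observed values and rule (a). Section 7.4.3.7 is silent. Treating it as an escape is the natural reading, but it is not stated.

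**Requiring uninterrupted castration is defensible.** Section 7.4.3.7 does spell out the castration condition as progression before escape, and some censoring at escape follows from the endpoint. A rule based only on the progression visit could count a PSA rise that began during an escape. This stands for observed escapes. It does not justify censoring on imputed failures, on gaps with castrate values on both sides, or before a death.

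**The PSA data are not lost altogether.** Time to PSA progression (7.4.3.6) has no escape censoring. That helps, but it omits deaths and is not alpha-protected.

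**Bias is not shown.** The 6% and 4% are planning values for the whole population, not for metastatic men. Unequal, informative censoring is possible but unquantified. Censoring at discontinuation also overlaps the planned 15% dropout.

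**On Week 49**, a planning rate for confirmed events may already be net of confirmation. Progression without a PSA decline has no stated confirmation requirement, and an unscheduled sample late in the Week 49 window (to Day 365) could confirm a rise.

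**Conclusion.** The concern holds as a mismatch between the CRFS definition and its censoring rule. Single unconfirmed values, back-dated escapes and gap censoring end follow-up permanently, and so can remove castrate-level progressions and later deaths that the definition includes. Whether Week 5 failures do the same is left open, so two programmers could derive different dates for an alpha-protected endpoint.

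The cost in events is small: about 2.5 to 5 of 107 and 1 to 2 power points, given exponential times and the SAP's 6% and 4%. A larger loss needs an assumed rate of missing Week 5 samples. The Week 49 point is separate and potentially larger (about 100 events, or 96 to 98 with escape censoring; power about 79 to 81% against 83%), but it applies only if the 60% rate does not already allow for confirmation. This should be corrected, but it does not undermine the endpoint.

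**What to change.** In Section 7.4.3.7:
1. State that imputed failures (missing Week 5 sample, escapes back-dated to a missed visit) and missed-visit gap censoring do not censor CRFS, and state how an observed non-castrate Week 5 value is treated.
2. Count on-treatment deaths as events regardless of an earlier escape, as the definition says.
3. Add a sensitivity analysis that judges *while castrated* by the testosterone result at the progression visit. Alternatively, make that the main analysis and keep the current rule as the sensitivity analysis. Either order is acceptable if fixed before the CRFS data are analysed.

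In Section 2.2, state whether the 60% rate already allows for Week 49 rises that cannot be confirmed. If it does not, restate the expected events as about 100 (about 96 to 98 with escape censoring) with the matching power.

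The cost is SAP wording and one derived variable. Testosterone and PSA are already sampled on the same schedule (Section 2.1), so no new data are needed. The stated event count and power may become slightly less favourable.
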